11. EVALUATION AND CALCULATION OF VARIABLES

11.1 Calculation or derivation of efficacy variable(s)

11.1.1 Primary efficacy variable

The primary efficacy variable of this study is the time from randomization to occurrence of gastric or duodenal ulcers.

11.1.2 Secondary efficacy variables

The secondary efficacy variables of this study include:

- Presence/absence of gastric and/or duodenal ulcer until Weeks 12, 24, 36, 48, 60 and 72 after randomisation
- Degree of gastric mucosal lesion according to the modified LANZA score at Weeks 12, 24, 36, 48, 60 and 72 after randomisation
- Presence/absence and severity of RE evaluated by LA classification at Weeks 12, 24, 36, 48, 60 and 72 after randomisation
- Presence/absence and severity of gastrointestinal symptoms assessed by the investigator(s) at each visit

11.2 Calculation or derivation of safety variable(s)

Safety variables are as below.

- Adverse events
- Clinical laboratory values
- Vital signs (blood pressure and pulse rate)

11.2.1 Other significant adverse events (OAE)

During the evaluation of the AE data, an AstraZeneca medically qualified expert will review the list of AEs that were not reported as SAEs and discontinuations of investigational product due to AE (DAEs). Based on the expert's judgement, significant adverse events of particular clinical importance may, after consultation with the Global Patient Safety Physician, be considered OAEs and reported as such in the Clinical Study Report. A similar review of laboratory/vital signs (blood pressure and pulse rate) data will be performed for identification of OAEs.

Examples of these are marked haematological, biochemical and other laboratory abnormalities, and certain events that lead to intervention (other than those already classified as serious), dose reduction or significant additional treatment.

11.3 Calculation or derivation of pharmacogenetic variables

Pharmacogenetic variables are as below.

Genotypes of CYP2C19

- Homo EM
- Hetero EM
- PM

This variable will be used to investigate the effect of CYP2C19 polymorphism on the efficacy of D20.

12. STATISTICAL METHODS AND SAMPLE SIZE DETERMINATION BY ASTRAZENECA

12.1 Description of analysis sets

All analysis sets will be determined before unblinding the study.

12.1.1 Efficacy analysis set

For analysis of the efficacy data, two analysis populations will be set, namely; a full-analysisset (FAS) and a per-protocol-set (PPS), and the primary statistical analysis of all efficacy data will be performed using the FAS.

The FAS will consist of all subjects randomized to the study who took at least one dose of study medication and who had no active/current gastric or duodenal ulcer at baseline. The PPS will be a subset of subjects from the FAS, and those who comply restrictions of the study treatment without any serious protocol deviations or violations.

12.1.2 Safety analysis set

All subjects who received at least one dose of randomised investigational product and for whom any post-dose data are available will be included in the safety population. Throughout the safety results sections, erroneously treated subjects (e.g., those randomised to treatment A but actually given treatment B) will be accounted for in the actual treatment group.

12.2 Methods of statistical analyses

A comprehensive Statistical Analysis Plan (SAP) will be prepared before unblinding of the data. A significant level of p<0.05 (two-tailed) will be used, in principle, for statistical tests and interval estimation.

All statistical analyses in this study will be performed by Statistics and Programming Department of AstraZeneca K.K. using the SAS software.

12.2.1 Primary variable

The primary variable of this study is the time from randomisation to a occurrence of gastric and/or duodenal ulcer. Both FAS and PPS will be used for the analyses of the primary variable, but the primary analysis will be based on the FAS. In addition, a secondary analysis for the primary variable will be done using the FAS excluding the data of subjects who are judged not to have an ulcer scar by the central evaluation committee at baseline (see Section 12.4). In this analysis, the evaluation of the central committee for the presence/absence of gastric and/or duodenal ulcer after randomisation will be used.

If a occurrence of gastric and/or duodenal ulcer is confirmed by EGD, then the occurrence will be defined as an event. The time from the randomisation to the occurrence of the peptic ulcer will be analysed using the Kaplan-Meier method and shown as graphs. For subjects who have no occurrence of peptic ulcer throughout the study, they will be treated as censored at the timing of the last EGD. The time-to-event curves will be compared between D20 and placebo using a log-rank test.

As a secondary analysis, the primary variable will also be analysed based on a Cox proportional hazard model including effects of sex, age, *H. Pylo*ri status, dose of LDA and CYP2C19.

12.2.2 Secondary variables

12.2.2.1 Presence/absence of gastric and/or duodenal ulcers for up to 12, 24, 36, 48, 60 and 72 weeks after randomisation

Both FAS and PPS will be used for the analyses of these variables as well as the primary variable. In addition, a secondary analysis for these variables will be done using the FAS excluding the data of subjects who are judged not to have an ulcer scar by the central evaluation committee at baseline. In this analysis, the evaluation of the central committee for the presence/absence of gastric and/or duodenal ulcer after randomisation will be used.

Ulcer-free rates for each treatment group at Weeks 12, 24, 36, 48, 60 and 72 after randomisation will be calculated by the following two methods

Ulcer-free rate by the Kaplan-Meier method

The ulcer-free rates at Weeks 12, 24, 36, 48, 60 and 72 for each treatment group will be obtained from the Kaplan-Meier plot prepared in the analysis of the primary variable. These ulcer-free rates are defined as "estimated ulcer-free rates". The two-sided 95% CIs of the estimated ulcer-free rates will be calculated using the Greenwood formula. Subgroup analyses for the estimated ulcer-free rates will be done for the following factors.

- Sex (Male, Female)
- Age (<65, 65-74, ≥75)
- *H. Pylo*ri status (Positive, Negative, Not evaluable/Sample lost)

- Dosage of LDA ($\leq 100 \text{ mg}$, > 100 mg)
- Concomitant use of steroidal agent(s) (Yes, No)
- Concomitant use of antiplatelet drug(s) (Yes, No)
- Genotypes of CYP2C19 (Homo EM, Hetero EM, PM)
- Primary disease (Angina cordis, ...)

Ulcer-free rate by EGD performed at each time point

For each time point of Weeks 12, 24, 36, 48, 60 and 72 after randomisation, the number of subjects who had a occurrence of gastric and/or duodenal ulcer confirmed by EGD at the corresponding time point or before will be calculated and the proportions of the subjects in the analysis sets will be obtained. These proportions will be defined as "observed ulcer-free rate". The 95% CIs of the observed ulcer-free rates will be calculated using the Newcombe-Wilson score method without continuity correction (Newcombe RG 1998). Subgroup analyses for the above factors will be done for the observed ulcer-free rates and thee 95% CIs.

12.2.2.2 Degree of gastric mucosal lesion by modified LANZA score at Weeks 12, 24, 36, 48, 60 and 72 after randomisation

These variables will be analysed using the FAS only. In addition, these variables will be analysed using the FAS excluding the subjects who were judged not to have an ulcer scar by the central evaluation committee at baseline.

Degree of gastric mucosal lesion will be evaluated using the modified LANZA score based on the results of EGD at pre-dose and at Weeks 12, 24, 36, 48, 60 and 72 after randomisation.

A cross table of the modified LANZA scores at pre-dose and each time point of post-dose will be prepared for each treatment group. In addition, scores at pre-dose, Week 12, 24, 36, 48, 60 and 72 and the changes from pre-dose to the time points at post-dose will be summarised for each treatment group using descriptive statistics.

12.2.2.3 Presence/absence and severity of reflux esophagitis at Weeks 12, 24, 36, 48, 60 and 72 after randomisation

These variables will be analysed using the FAS only. In addition, these variables will be analysed using the FAS excluding the subjects who were judged not to have an ulcer scar by the central evaluation committee at baseline.

Presence/Absence and the severity of RE will be evaluated using the LA classification based on the results of EGD at pre-dose and at Weeks 12, 24, 36, 48, 60 and 72 after randomisation.

The number and the proportion of subjects for each LA classification at Weeks 12, 24, 36, 48, 60 and 72 will be summarised for each treatment group.

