12.3 Determination of sample size

The sample size for this study was selected to be consistent with the research hypothesis as described in Section 1.2.

The primary variable of this study is the time from randomisation to occurrence of peptic ulcer. The result of a phase III study (D961FC00003) was used to estimate the occurrence rates of peptic ulcer at 6 months for D20 and placebo. The event rates for peptic ulcer at 6 months were 1.5% for D20 and 7.4% for placebo, respectively.

In order to detect a difference in time to occurrence of peptic ulcer between D20 and placebo with two-sided 2.94% significance level and >90% power, assuming a recruitment period of 12 months and a minimum follow-up of 6 months; i.e. the total length of study is estimated to be 18 months, at least 36 events will be required. To get the number of events during the period in total 426 subjects (213 subjects per group) will be randomised in the study taking 15% of subjects who may discontinue the study without an event into consideration.

The final analysis of the primary variable will be performed when 36 events are observed. The nominal 2-sided significance level for all analyses will be 5%, except for the primary variable, where the nominal significance level will be adjusted using the Pocock-like alphaspending function with Lan-DeMets approach to allow for a single interim analysis.

In this study, at least 100 subjects who are randomised to D20 will continue taking investigational product for one year to obtain long-term safety data because one-year safety data from at least 100 subjects are required according to the ICH E1 guideline "The Extent of Population Exposure to Assess Clinical Safety for Drugs Intended for Long-Term Treatment of Non-Life-Threatening Conditions".

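### The Greenwood interval for the Kaplan-Meier ulcer-free rate shrinks to 100%–100% in any group with no ulcer, and the protocol has no rule for that case (minor)

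*Protocol*

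**What the plan says.** Section 12.2.2.1 of the protocol defines two ulcer-free rates per treatment group at Weeks 12, 24, 36, 48, 60 and 72.

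- **Estimated rate**, read from the Kaplan-Meier curve: "The two-sided 95% CIs of the estimated ulcer-free rates will be calculated using the Greenwood formula". The next sentence is "Subgroup analyses for the estimated ulcer-free rates will be done for the following factors", and the list includes "Genotypes of CYP2C19 (Homo EM, Hetero EM, PM". No transformation and no zero-event rule is given.
- **Observed rate**, a proportion of the subjects in the analysis set: its 95% intervals are "calculated using the Newcombe-Wilson score method without continuity correction". Here the subgroup intervals are explicit: "Subgroup analyses for the above factors will be done for the observed ulcer-free rates and thee 95% CIs".

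Section 12.3 gives the planning figures: "The event rates for peptic ulcer at 6 months were 1.5% for D20 and 7.4% for placebo, respectively", and "in total 426 subjects (213 subjects per group) will be randomised in the study". Section 2.3 makes the CYP2C19 question exploratory.

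**The concern.** The Greenwood variance is built from the observed events. With none, it is zero, and the method reports a rate of 100% with no uncertainty, for 28 subjects or for 213. D20 is expected to produce few ulcers, so this is a likely outcome early in the trial, above all in small subgroups.

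A PM cell of about 38 subjects could then be tabulated as 100% (95% CI 100–100). A reader would take that as certain protection in that genotype. The observed-rate table would show 90.8–100% for the same cell and week if all 38 are in the analysis set.

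**Working it through.** The protocol states no genotype cell size and no target precision, so there is no stated figure of that kind to reproduce. The check uses its planning inputs.

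**Inputs from the protocol**
- D20 ulcer rate at 6 months: 1.5% (section 12.3). Table 1 in section 1.3.1 lists 1.1% for D20 in the same source study, with 1.5% under the 40 mg dose, so 1.1% is the lower sensitivity value.
- 213 subjects per arm and 15% discontinuing without an event (section 12.3). 213 × 0.85 = 181.
- PM share across the reports cited in section 1.3.2: 13% to 23%. Base case 18%.

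**Assumptions**
- Constant hazard, the same D20 rate in every genotype, and no censoring.
- Hardy-Weinberg split of the remaining genotypes. With PM 18%, q = √0.18 = 0.424. Cells: PM 0.18 × 213 = 38; hetero EM 2 × 0.424 × 0.576 × 213 = 104; homo EM 0.576² × 213 = 71.
- An upper sensitivity rate of 3% per 6 months (double the planning rate), because this trial enrols patients with an ulcer history.

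**Step 1: degeneracy.** Var(S) = S² × Σ d/[n(n − d)]. If every d = 0, then S = 1 and Var = 0, so the interval is 100–100%. A log transformation has the same zero variance, and log(−log S) is undefined at S = 1, so neither repairs it.

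**Step 2: chance of no ulcer.** The rate by week t is r = 1 − (1 − p)^(t/26). At p = 0.015, r = 0.0070 at Week 12 and 0.0139 at Week 24. P(no ulcer) = (1 − r)^n.

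| Group (n) | Week 12 | Week 24 |
|---|---|---|
| PM (38) | 77% | 59% |
| Homo EM (71) | 61% | 37% |
| Hetero EM (104) | 48% | 23% |
| Whole D20 arm (213) | 23% | 5% |

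Expected empty genotype cells out of 3: 1.9 at Week 12, 1.2 at Week 24 and 0.8 at Week 36. P(at least 2 empty) = 0.68, 0.34 and 0.16.

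**Step 3: coverage.** Without censoring, the untransformed Greenwood interval equals the binomial Wald interval, so coverage can be enumerated exactly.
- Week 12, for PM, homo EM, hetero EM and the whole arm: Greenwood 23%, 39%, 52% and 77%; Wilson 97%, 91%, 96% and 94%. These Greenwood figures are just one minus the zero-event chance, so they restate Step 2.
- Week 24, for the three cells in the same order: Greenwood 41%, 63% and 76%; Wilson 90%, 92% and 94%.

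**Step 4: sensitivity**
- PM share 13–23% and 181–213 subjects, P(at least 2 of 3 cells empty). At 1.5%: Week 12 0.68–0.75, Week 24 0.34–0.43. At 1.1%: Week 12 0.79–0.84, Week 24 0.50–0.59.
- 3% per 6 months, Week 12: PM 59%, homo EM 37%, hetero EM 23%, or 1.2 of 3 cells; whole arm 5%.

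**Step 5: what a score interval gives with no ulcer.** Lower Wilson limit = n/(n + 1.96²). For n = 38: 38/41.84 = 90.8%. For n = 71: 94.9%. For n = 104: 96.4%. The exact lower limits are nearly the same (90.7%, 94.9%, 96.5%).

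**The case against.** **This belongs in the analysis plan.** Greenwood is a standard choice. Transformation, truncation at 100% and the display of empty cells are usually settled in the SAP, which is not to hand. That holds for transformation and truncation: one might infer that the protocol prescribes limits above 100% when there are one to three ulcers, but this assumes an untransformed interval that the text does not specify. It does not hold for the empty group, because the protocol names the method and no usual transformation rescues it.

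**A sound interval is already planned.** The observed rate gets a Wilson interval in the same genotype cells at the same weeks. This is the strongest point and it limits the damage. Two methods side by side are also not a contradiction in the plan. But the observed rate keeps subjects who leave early without an ulcer in the denominator. The Kaplan-Meier rate is the one that handles censoring, and it carries the faulty interval.

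**Intervals by genotype are not stated for the Kaplan-Meier rate.** Correct. The subgroup sentence directly follows the Greenwood sentence, so this is the natural reading, but only the observed-rate subgroups have intervals expressly attached. The whole-arm problem does not depend on that reading.

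**Nothing hangs on these intervals.** Correct. The primary test is log-rank, CYP2C19 also enters a Cox model (section 12.2.1), and no boundary or decision uses them.

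**Conclusion.** The defect is real and minor. As written, any group without an ulcer gets a zero-width Greenwood interval. At the planning rate the Week 12 chance is about 23% for the whole D20 arm and, if intervals are shown by genotype, 77% (PM), 61% (homo EM) and 48% (hetero EM).

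A reader might infer that most genotype cells will be empty throughout the early visits. At the planning rate that holds for Week 12 only. At Week 24 about 1.2 of 3 cells are expected to be empty and only PM is more likely than not. At 1.1% per 6 months Week 24 is about even (1.5 of 3 in the base case), and at 3% empty cells are a minority even at Week 12.

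Nor do the documents support saying that a genotype comparison is made anti-conservative: section 12.2.2.1 plans no test between genotypes from these intervals. What is affected is how descriptive secondary and exploratory tables will be read. The figures rest on a constant hazard, equal D20 rates across genotypes, no censoring and a Hardy-Weinberg split.

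**What to change.** In section 12.2.2.1, state that the 95% interval of the Kaplan-Meier ulcer-free rate will be a score-type interval using the effective sample size implied by the Greenwood variance. Where there is no event, that size is not defined, so n is the number still at risk.

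The minimum alternative is to keep Greenwood and state that, where no event has occurred by the time point, it is replaced by a Wilson or exact interval with n equal to the number still at risk.

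Apply the rule to the whole arm and to every subgroup for which an interval is shown, and say whether the Kaplan-Meier subgroups, including CYP2C19, will carry intervals. The cost is one or two sentences, a few lines of code and wider intervals in low-event groups. Sample size, the primary test and the interim analysis are unaffected.

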3.1 Overall study design and flow chart

This study is designed as a multinational, multicenter, randomized, double-blind, parallelgroup (2 groups), placebo controlled, Phase III study involving patients with a history of gastric and/or duodenal ulcers receiving daily LDA therapy. A total of 426 patients with a history of gastric and/or duodenal ulcers with ulcer scar confirmed by the esophagogastroduodenoscopy (EGD) performed at screening will be randomized 1:1 to either D20 group or placebo group. The efficacy and safety of D20 or placebo will be assessed after up to 72-week oral administration based on the results of the EGD performed at Weeks 12, 24, 36, 48, 60 and 72 after randomisation to verify presence or absence of gastric and/or duodenal ulcers, modified LANZA score to evaluate the degree of gastric and/or duodenal mucosal lesion and presence/absence and severity of RE evaluated by LA classification, and investigator's assessment for presence/absence and severity of gastrointestinal symptoms performed every 4 weeks. In addition, the safety of the concomitant use of D961H and LDA for a long-term period will be confirmed. If development of gastric and/or duodenal ulcer was observed in 36 patients, data will be cut off and analysed. Therefore, it is speculated to administer the test product for up to 72 weeks, but the period of administration of test product may not reach 72 weeks. (See Figure 1)

When development of gastric and/or duodenal ulcer was observed in at least 18 patients and at least 250 patients were randomized, the interim analysis will be performed by an independent data monitoring committee (IDMC) following the data cut-off, data cleaning and data base lock for the analysis. IDMC will decide on a recommendation on continuing or discontinuing the comparative analysis based on the results of the interim analysis (See Section 12.2.3). If IDMC recommend to continue the study, a final comparative analysis will be performed when development of gastric and/or duodenal ulcer is observed in at least 36 patients following the data cut-off, data cleaning and the database lock.

The sponsor will count the number of subjects in the D20 groups who have completed the tests at Visit 15 (Week 52) quickly after the completion of the comparative analysis (including the completion by the interim analysis).

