9.5 Study timetable and end of study

The end of the study is defined as 'the last visit of the last subject undergoing the study'.

The study may be terminated at individual centres if the study procedures are not being performed according to GCP, or if recruitment is slow. AstraZeneca may also terminate the entire study prematurely if concerns for safety arise within this study or in any other study with D961H or OPZ.

Planned duration of the study:

Study period: January 2010 (First subject in) to July 2011 (Last subject last visit)

Registration period: January 2010 (First subject in) to January 2011 (Last subject in)

Registration period is changed depending on accumulation speed of gastric and/or duodenal ulcer events.

The principal investigator will be notified when the subject randomisation has completed and required number of gastric and/or duodenal ulcer events are confirmed.

Discontinuation or suspension of the whole study programme

If AstraZeneca decides to prematurely terminate or suspend the study, the Principal Investigator, sub-investigator, the head of the institution (for Japan), and regulatory authorities should receive written notification of the reasons for the premature termination or suspension.

The Principal Investigator/sub-investigator will immediately notify the decision to the subjects, give appropriate medical treatment; take necessary measures, and record treatment or measures provided on the source documents.

Completion of the study (for Japan)

Upon terminating the study, the Principal Investigator/sub-investigator will report in writing the completion of the study as well as the summary of the results to the head of the study site in accordance with the institution's rules. The head of the study site, who is informed of the termination by the investigator, will provide a written notification of the results to the IRB and AstraZeneca.

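### The EGD-based observed ulcer-free rate is defined as the proportion with an ulcer, and its whole-analysis-set denominator counts subjects not followed to the week as ulcer-free

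*Protocol*

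**What the plan says.** Protocol 12.2.2.1 announces ulcer-free rates at Weeks 12, 24, 36, 48, 60 and 72 by two methods. The first reads them off the Kaplan-Meier curve, with Greenwood intervals. The second is based on the EGDs. It takes "the number of subjects who had a occurrence of gastric and/or duodenal ulcer confirmed by EGD at the corresponding time point or before", says that "the proportions of the subjects in the analysis sets will be obtained", and names those proportions the observed ulcer-free rate. Their 95% intervals are to be "calculated using the Newcombe-Wilson score method without continuity correction".

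Four other places bear on this:

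- Protocol 12.1.1 sets no follow-up condition for the main analysis set: "The FAS will consist of all subjects randomized to the study who took at least one dose of study medication" and who had no active ulcer at baseline.
- Protocol 3.1 makes the cut-off event-driven and warns that "the period of administration of test product may not reach 72 weeks".
- Protocol 9.5 staggers entry over a year: "Registration period: January 2010 (First subject in) to January 2011 (Last subject in"), with the last visit planned for July 2011.
- Protocol 12.2.1 says of subjects without an ulcer that "they will be treated as censored at the timing of the last EGD". This rule serves the Kaplan-Meier method. The EGD-based rate has no counterpart to it.

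**The concern.** The definition has two separate faults.

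The first is direction. The numerator counts subjects who had an ulcer, while the name says ulcer-free. A table programmed from that sentence would show the better arm with the lower so-called ulcer-free rate.

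The second is the denominator, and it remains after the direction is corrected. A subject who left without an ulcer at Week 20, or who was randomised only 30 weeks before the cut-off, is in the analysis set and is not an ulcer case. At Week 72 that subject therefore counts as ulcer-free, although nobody looked at Week 72. The later the week, the more such subjects there are. The rate is pushed upwards, and more so in the arm with more ulcers.

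The rate belongs to the first-listed secondary efficacy variable. It is to be produced for the FAS, the PPS and the centrally reviewed set, and again across eight subgroup factors.

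**Working it through.** The protocol gives no numerical value for this rate, so there is no stated figure to reproduce.

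**Inputs.** From Protocol 12.3: 6-month ulcer rates of 1.5% (D20) and 7.4% (placebo), 213 subjects per group, 12 months' recruitment plus 6 months' minimum follow-up, and 15% discontinuing without an event. From the study plan table: an EGD allowance of 14 days. Assumptions: constant hazards, uniform entry, 6 months = 26 weeks, and the 15% dropout spread exponentially over either 26 or 78 weeks, shown as a range. The 12-weekly EGD grid is not modelled.

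**1. Direction.** Taken literally, the 6-month rates are 1.5% and 7.4%; the ulcer-free rates are 100 − 1.5 = 98.5% and 100 − 7.4 = 92.6%. With whole subjects and Wilson 95% intervals:

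- D20, 3/213: 1.4% (0.5 to 4.1) as written; 98.6% (95.9 to 99.5) as intended.
- Placebo, 16/213: 7.5% (4.7 to 11.9) as written; 92.5% (88.1 to 95.3) as intended.

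**2. Who can reach the week.** With entry over 365 days and a cut at day 548, the share randomised early enough, before any dropout, is (548 − 7k)/365:

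- Week 48: 212/365 = 58%
- Week 60: 128/365 = 35%
- Week 72: 44/365 = 12%

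**3. Size of the overstatement.** Weekly ulcer hazard λ = −ln(1 − p)/26: 0.002957 on placebo and 0.000581 on D20. Dropout hazard μ = −ln(0.85)/78 = 0.002084 or −ln(0.85)/26 = 0.006251. With r = λ + μ, the expected share of the whole analysis set with an ulcer recorded by Week k is (λ/r)(1 − E), where

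- E = exp(−rk) for k ≤ 26;
- E = [exp(−26r) − exp(−rk)]/(52r) + [(78 − k)/52]·exp(−rk) for k > 26.

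Placebo, Week 72, slow dropout: r = 0.005041, λ/r = 0.5866, E = 0.7728, so 0.5866 × 0.2272 = 13.3% with ulcer and a complement of 86.7%. The ulcer-free probability under the same hazard is exp(−72 × 0.002957) = 80.8%.

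| Week | Placebo: complement of the written rate | Placebo: exp(−λk) | Overstatement (points) |
|---|---|---|---|
| 24 | 93.3 to 93.6% | 93.1% | 0.2 to 0.5 |
| 48 | 88.5 to 89.5% | 86.8% | 1.7 to 2.7 |
| 72 | 86.7 to 88.0% | 80.8% | 5.9 to 7.2 |

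The lower end of each range is dropout spread over 78 weeks, the upper end over 26 weeks. Overstatements were taken before rounding.

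On D20 at Week 72 the complement is 97.2 to 97.5% against 95.9%, an overstatement of 1.3 to 1.6 points. The D20 minus placebo difference at Week 72 is therefore 9.5 to 10.5 points, against 95.9 − 80.8 = 15.1.

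**The case against.** The inversion is plainly a slip of wording. The subheading, the lead-in sentence, the Kaplan-Meier rates beside it and the synopsis all point to an ulcer-free rate. A reader might infer that the plan would report placebo as better than D20. The documents do not support that as an intention; it follows only from one clause read against everything around it. The clause still needs correcting, because it is the operative definition.

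The rate is also called observed in contrast to estimated, so it can be defended as a deliberately crude figure next to a censoring-adjusted one, with details left to the announced SAP. That has some force. But the protocol is not silent here: it fixes numerator, denominator and name, and a SAP that follows it carries both faults forward.

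Three further inferences go too far:

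- That most subjects cannot have a Week 48 EGD. By entry date 58% can; the statement holds for Weeks 60 and 72 only.
- That the score interval is unsuitable. The Wilson interval for 1 − p is one minus the interval for p, so it turns round with the rate.
- That the denominator flatters D20. It shrinks the difference between the arms.

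It is also fair that the Week 72 figures extend 6-month rates at a constant hazard, which the protocol does not state, and that Weeks 12 and 24 are hardly affected.

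**Conclusion.** The point holds in two parts, as something that should be fixed.

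The inversion is explicit in the text and needs no assumption. The denominator fault follows from the plain wording and from an analysis set without a follow-up condition. Its size rests on the accrual, cut-off, dropout and constant-hazard assumptions above. It is negligible up to Week 24, modest at Week 48, and large enough at Weeks 60 and 72 to make the crude rate a poor summary.

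A reader might infer that the trial's conclusion is at risk. It is not. The primary comparison is a log-rank test, the interim analysis uses time to ulcer, the Kaplan-Meier rates are correctly oriented and censored, and 12.2.2.1 specifies no between-group test of the observed rate.

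**What to change.** Change the EGD-based definition in 12.2.2.1 as follows:

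1. Make the numerator the subjects with no ulcer confirmed by EGD at or before the week.
2. For Week k, limit numerator and denominator to analysis-set subjects randomised at least k weeks, plus the 14-day EGD allowance, before the data cut-off. This selects on entry date and not on outcome. A denominator of subjects with an EGD at that week or an earlier ulcer would over-weight ulcers.
3. Within that denominator show three categories: ulcer by the week, ulcer-free at the week, and left the study without an ulcer before the week. Do not count the third as ulcer-free.
4. For Weeks 60 and 72 rely on the Kaplan-Meier estimated ulcer-free rates, which are already planned.

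The cost is a few sentences of text, smaller denominators and wider intervals at late weeks. At Week 72 about 26 subjects per arm remain (0.12 × 213), or about 18 once the 14-day allowance is taken off (30/365 × 213), so subgroup splits of the observed rate there would carry little information. Because dropouts stay in the denominator, the ulcer-free share is a cautious figure and should be read with the dropout share beside it.
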